Statistical Considerations	
Up to 5% of the population of Europe is thought to have diabetes. About 30m surgeries are performed in Europe per annum, therefore perhaps 1.5m diabetics have surgery in Europe per annum. It is proposed to evaluate a pragmatic sample of 5,000 European diabetic patients across at least 50 centres in a minimum of 10 nations.
 
Centres undertaking surgery for diabetic patients will be invited to contribute patients. It is envisaged that this target number would be enrolled over a two-year period from initial roll-out, with up to a further 12 months needed for final data acquisition, cleaning and analysis.
 
A sample size of 5,000 should be sufficient to avoid over-fitting and variance inflation for up to 63 factors or interactions. In addition, a sample size of 5,000 will have 90% power to find a small standardised difference of 0.10 as significant at <math>P < 0.05</math> for up to 63 independent hypotheses in comparing subsets of interest.

Risk-Benefit analysis	
There is no risk to patients participating in this study other than any risk associated with their perioperative care. Individual patients will not benefit from the study, but the knowledge gained from the overall evaluation will inform best practice in this previously under-researched field.

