### 4.2 Study centres and role of national and local PIs

Any hospital in Europe (as defined by the World Health Organisation) is welcome to participate as a study centre. Non-European centres may be accepted upon request to the SC. Centres will be asked to enrol a minimum of 45 patients (up to 200) over a recruitment period of up to 18 months from the date of the centre's registration with ESAIC. No more than one quarter (25%) of a centre's patients can be day cases (ambulatory anaesthesia). Study centre registration occurs online via the dedicated "Call for Centres form" on the ESAIC website. Within the overall Europe-wide period of recruitment planned for MOPED (at least 18 months), the start of recruitment for individual centres is soon as possible after centre registration with ESAIC, provided that there is prior IRB approval. Recruitment will continue until enrolment of the planned sample size (n=5,000).

National coordinating investigators are anaesthesiologists appointed by ESAIC and the SC to lead the project within individual countries and their responsibility includes:

- Identify centres in their country and recruit local PIs in participating hospitals;
- Assist in the translation of required study documents;
- Ensure that all necessary national or regional regulatory approvals are in place prior to start of patient inclusion;
- Assist and train the Local PI and monitor the conduct of the study according to ICH-GCP;
- Ensure good communication with ESAIC headquarters and the participating sites in his/her countries during all study steps including data cleaning.

Local PI may be anesthesiologists, surgeons or diabetes physicians working in perioperative medicine in each participating institution who will have the following responsibilities:

- Provide leadership for the study in their institution;
- Ensure all relevant regulatory/ethical approvals are in place for their institution;
- Ensure adequate training of all relevant staff prior to data collection;
- Supervise enrolment, daily data collection, and assist with problem solving;
- Adjudicate events
- Ensure timely completion of eCRF, follow-up assessments, and data cleaning queries. The Local PI is the main person responsible for ensuring integrity of data collection. By signing the data on eCRF Local PI confirms the data integrity;
- Communicate with ESAIC headquarters and the relevant National Coordinating Investigator during all study steps including data cleaning.

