## 7. STATISTICAL METHODOLOGY

### 7.1 Sample size estimation

It is proposed to evaluate a pragmatic sample of 5,000 European diabetic patients across at least 50 centres in a minimum of 15 nations. It is expected that this should be sufficient for the main epidemiological aspects of this study. It is envisaged that this target number would be enrolled over a two-year period from initial roll-out, with up to a further 12 months needed for final data acquisition, data cleaning and analysis. A sample size of 5,000 should be sufficient to avoid over-fitting and variance inflation for 50 to 70 factors and interactions based on the conventional square root or 100 values per variable respectively. In addition, a sample size of 5,000 will have at least 90% power to find a small standardized difference of

0.15 as significant at  $P < 0.05$  (Bonferroni corrected at  $P < 0.0007$ ) for up to 70 independent hypotheses and in comparing subsets of interest.

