## 7.3 Planned analyses

### 7.3.1 Main analysis

The aim of this research is to describe and quantify the epidemiology of the perioperative management of diabetic patients in Europe. Descriptive statistics such as mean (SD), median [interquartiles, range] and frequencies (%) will be presented as appropriate. The precision of the estimates will be reported with 95% confidence intervals to show the prevalence and incidence rates of diabetic phenotypes and major adverse events and complications.

The primary outcome measure is Days at Home at 30 Days (DAH-30).

Secondary outcomes include: Comprehensive Complications Index (CCI) score, based on Clavien-Dindo scale and the QoR-15 instrument measuring quality of recovery, taken only in patients who remain in hospital for Day 1 postoperative.

Secondary outcomes also include 30-day mortality, length of hospital stay, incidences of specific major adverse events (MI, MINS, AKI, PPC, CVA, PE, DVT and surgical site infection (SSI).)

Univariate analyses will be used to help identify variables of potential interest for multivariable analyses, in addition to stepwise selections. Robust multivariable regressions using maximum likelihood estimation (MLE), including Poisson and negative binomial, will be used to identify significant associations. Specific factors, or subsets of interest, will be investigated further using linear mixed models with MLE. Binary and categorical outcomes, such as occurrence of a postoperative pulmonary complication (PPC) will be analysed using multivariable logistic regression, survival analysis and Cox proportional hazards regression as appropriate.

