### 7.3.2 Datasets to be analysed

Data from all participants will be analysed with respect to completeness of data entry for all variables in an pseudonymised format. Patients will be nested within centre and stratified by country for relevant epidemiological purposes.

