### 7.3.3 Handling of missing data

Analyses will be performed on the observed data. Data missing at random exceeding 10% may be imputed and models will be re-analysed as sensitivity analyses. Linear mixed models with MLE will be used as these are relatively robust with missing longitudinal data compared to least squares methods such as repeated measures analysis of variance (ANOVA). Exact multivariable logistic regression with Firth penalised MLE will be used for sparse and missing data as practical.

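### Naming maximum likelihood for the linear mixed models understates between-centre variance if country enters as fixed strata; REML avoids this at no cost (minor, conditional)

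*Protocol*

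**What the plan says.** Section 7.3.1 of the protocol, after the Poisson, negative binomial and other regressions, adds a follow-up step: particular factors or subsets "will be investigated further using linear mixed models with MLE". Section 7.3.3 repeats the estimator and gives its reason: "Linear mixed models with MLE will be used as these are relatively robust with missing longitudinal data compared to least squares methods". REML is neither mentioned nor excluded. No test statistic, reference distribution or degrees-of-freedom method is given.

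On structure, section 7.3.2 states: "Patients will be nested within centre and stratified by country for relevant epidemiological purposes". It does not say whether country is a fixed or a random effect in a model.

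On numbers, section 7.1 plans 5,000 patients "across at least 50 centres in a minimum of 15 nations", while the synopsis has them "across at least 50 centres in a minimum of 10 nations". Section 4.2 sets 45 to 200 patients per centre. Research question 1 in the synopsis asks whether management practice differs between centres and between nations, and section 2.9 gives the possible effect of that variability on outcome as part of the rationale.

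**The concern.** ML estimates a variance as if the fixed effects were known. At the patient level, with 5,000 observations, this costs nothing. At the centre level the sample is the number of centres, and each country term or centre-level covariate uses up part of it. If many such terms are fitted, the between-centre variance comes out too small, standard errors for centre-level factors come out too short, and associations with centre-level practice look more certain than they are. The relative error is largest at the Bonferroni threshold of section 7.1.

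The reason given in section 7.3.3 does not favour ML over REML. Both are likelihood methods, and the advantage over least squares with incomplete longitudinal data is common to both.

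**Working it through.** **Inputs.** Centres J: at least 50 (section 7.1). The centre-size limits of section 4.2 alone would allow 5,000/200 = 25 to 5,000/45 = 111, so the plan's range is 50 to 111. Nations: at least 15 (section 7.1) or at least 10 (synopsis). Threshold: 0.05/70 = 0.000714, which reproduces the stated 0.0007. The between-centre intraclass correlation (ICC) is not in the document; 0.02, 0.05 and 0.10 are assumed.

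**Closed form, balanced centres.** Let p be the number of centre-level fixed parameters. ML estimates the variance of a centre mean at (J − p)/J of its true value. The type I error of a Wald test against the normal reference is therefore 2·P(t with J − p df > z·√((J − p)/J)).

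With 50 centres, 15 fixed country terms and one null centre-level factor, p = 16 and 34 df remain:
- Variance ratio 34/50 = 0.68; standard-error ratio √0.68 = 0.825.
- At nominal 5%: 1.96 × 0.825 = 1.616, and 2·P(t34 > 1.616) = 11.5%.
- At nominal 0.0714%: 0.86%, about 12 times nominal.
- ML likelihood-ratio test, 2·P(t34 > √(34·(exp(c/50) − 1))), where c is the chi-square critical value on 1 df: 10.9% and 0.56%. The inflation is therefore not peculiar to Wald tests.

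| Setting | df/J | ML Wald, 5% | REML, normal reference, 5% | ML Wald, 0.0714% |
|---|---|---|---|---|
| 50 centres, 15 fixed countries | 34/50 = 0.68 | 11.5% | 5.8% | 0.86% |
| 50 centres, 10 fixed countries | 39/50 = 0.78 | 9.1% | 5.7% | 0.48% |
| 110 centres, 15 fixed countries | 94/110 = 0.85 | 7.3% | 5.3% | 0.23% |
| 50 centres, no country terms | 48/50 = 0.96 | 6.1% | 5.6% | 0.18% |

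**Simulation.** Random-intercept models were fitted by ML and REML to unequal centre sizes totalling about 5,000, with a null binary centre-level factor.
- 50 centres, 15 fixed countries, 3,000 runs per ICC: ML error 11.1% to 12.2%; REML with normal reference 5.7% to 6.0%; REML with a t reference 4.8% to 5.2%.
- In the same runs the between-centre variance was 0.50 (ICC 0.02), 0.61 (0.05) and 0.65 (0.10) of the truth under ML, and 0.99 to 1.00 under REML. These ratios fall below 0.68 because 0.68 applies to the whole variance of a centre mean, including sampling error. For example, at ICC 0.10 with 5,000/50 = 100 patients per centre: 0.68 × (0.10 + 0.90/100) − 0.90/100 = 0.065, which is 0.65 of 0.10.
- 50 centres, 10 fixed countries, ICC 0.05: ML 9.4%.
- Country left out, ICC 0.05: ML variance 0.95 of true; ML 5.2%, REML with normal reference 4.8%.
- Country random, ICC 0.05, 1,000 runs: ML variance 0.97 of true; ML 7.0%, REML with normal reference 6.7%.

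**Patient-level factor.** With N = 5,000 and 50 centres, the standard-error ratio is √((4,950 − p)/4,950). For p = 2 it is 0.9998 and the error is 5.01%; for p = 70 it is 0.993 and the error is 5.17%.

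**The case against.** The strongest reply is that the material scenario is not written in the protocol. Section 7.3.2 could mean descriptive stratification or a random country level, and in either case the ML–REML gap is 0.3 to 0.5 points. The subsets listed in sections 3.1 and 7.3.4 (diabetes type, HbA1c stratum, anaesthetic technique) are recorded per patient. No section assigns a centre-level practice factor to the mixed models, and the objective in section 3.1 is to document management, which needs no such test. Fifty centres is a floor. MLE also reads as generic wording: section 7.3.3 sets it against least squares, not against REML. The choice of reference distribution is commonly left to the SAP.

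Most of this stands, and it limits the point. A reader might infer that the planned mixed models will double the false-positive rate, or that the listed subgroup comparisons are unsafe. The document supports neither: the first needs fixed country terms, a centre count near the minimum and a centre-level factor, and the second is contradicted by the patient-level figures.

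Two things remain. The estimator is stated twice, so this is a named method rather than a detail left open. And the downward bias in between-centre variance under fixed country strata depends on no choice of test, while that variance is a natural measure of the variation the synopsis asks about.

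**Conclusion.** The point holds as a minor, conditional one. ML is the less suitable estimator for between-centre variance and for centre-level or country-level terms, and the stated reason for it applies equally to REML.

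If country is fitted as fixed strata with 50 centres, type I error for a centre-level factor is about 11% (15 nations) or about 9% (10 nations) instead of 5%; with 110 centres and 15 nations it is about 7%. In that setting most of the excess comes from ML, since REML with a normal reference gives 5.8%. If country is random or absent, changing the estimator gains at most about half a percentage point.

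These figures assume normal or chi-square reference tests and one centre-level factor. The simulated figures also assume an ICC of 0.02 to 0.10, over which the error rates hardly change. The patient-level result assumes factors that vary within centres. The Poisson, negative binomial, logistic and Cox analyses are not touched by this point.

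**What to change.** In sections 7.3.1 and 7.3.3, replace the reference to MLE for linear mixed models with: *linear mixed models estimated by REML, with Kenward-Roger or Satterthwaite degrees of freedom, for between-centre variance and for any centre-level or country-level term*. Keep ML only for likelihood-ratio comparison of fixed-effect structures. Because that test is itself liberal when many country terms are fitted (10.9% above), take the reported P values and intervals for centre-level terms from the REML fit.

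In section 7.3.2, state whether country is a fixed or a random effect. Reconcile the minimum number of nations between the synopsis (10) and section 7.1 (15), since the number of country terms follows from it.

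The cost is a wording change and a software option. No further data or patients are needed, and patient-level results are practically unchanged. Intervals for centre-level factors will be wider where country is fitted as fixed strata.

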### 7.3.2 Datasets to be analysed

Data from all participants will be analysed with respect to completeness of data entry for all variables in an pseudonymised format. Patients will be nested within centre and stratified by country for relevant epidemiological purposes.

### 7.3.3 Handling of missing data

Analyses will be performed on the observed data. Data missing at random exceeding 10% may be imputed and models will be re-analysed as sensitivity analyses. Linear mixed models with MLE will be used as these are relatively robust with missing longitudinal data compared to least squares methods such as repeated measures analysis of variance (ANOVA). Exact multivariable logistic regression with Firth penalised MLE will be used for sparse and missing data as practical.

### 7.3.4 Ancillary analyses

In addition to the sensitivity analyses as described, the effects of pre-defined subsets will be investigated. These subsets will include: DM1, DM2, DM3, MODY and LADA diabetic patients; Strata of glycaemic control, HbA1c <53, HbA1c 53-69 and HbA1c >69 mmol/mmol;

Anaesthetic techniques, inhalational (IA) versus total intravenous (TIVA), regional (RA) versus general (GA), combined GA and RA versus GA alone.

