## SYNOPSIS

Principal Investigator	[name] [name], Mater University Hospital, University College Dublin, Ireland
Title	Management and Outcome after Perioperative Care among European Diabetic Patients (MOPED)
Short Title	MOPED
Trial Registration	NCT04511312
Protocol Version	V 1.0
Background & Rationale	
Diabetes is common (about 20m patients in Europe), and patients have more surgical interventions than the general population. There are plausible pathophysiology and clinical mechanisms that diabetic patients are at increased risk of postoperative complications. When postoperative complications occur in the general population, they increase one-year mortality or major adverse events up to one year later. This is likely to be worse in diabetic patients. There is variation in practice guidelines in different countries in the perioperative management of diabetic patients undergoing major surgery, and whether this may affect postoperative outcome has not been investigated on a large scale. Neither is it known whether postoperative outcome differs depending on subgroups of diabetic patients, particularly whether different strata of preoperative glycaemic control affects outcome. If confirmed in this study, personalised perioperative management of diabetic patients may be enabled.

Objectives	
Main Objectives: To conduct the first major European epidemiological study on the perioperative management of diabetic patients undergoing surgery and their 30-day postoperative patient-centered outcome;
 
To evaluate subgroup outcomes, particularly strata of preoperative glycaemic control.
 
Specific Objectives: To address the following research questions: 1. What is the epidemiology of diabetic patients undergoing surgery across Europe: Are there major variations in perioperative glycaemic control? Does management practice vary between centres and between nations? 2. What is the extent and patient-centered impact of postoperative complications among diabetic patients up to 30 days after surgery in Europe? 3. To undertake sub-group analysis comparing these outcomes among *Diabetes Mellitus Type 1, Diabetes Mellitus Type 2, and other diabetic patients; *Patients with different strata (levels) of glycaemic control, i.e. HbA1c <53, HbA1c 53-69 and HbA1c >69 mmol.mol; *Patients who received different anaesthetic techniques: -Volatile versus total intravenous anaesthesia; regional versus general anaesthesia (GA) and

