## 2.9 Rationale for the research project

National bodies in Europe and elsewhere differ in their guidelines on management of diabetic patients undergoing surgery and small observational studies confirm wide variability in practice and perioperative management between centers.[1-3] Whether this variability in practice affects postoperative outcome among diabetic patients in countries across Europe has not been investigated.

Further, our sub-group analysis will provide novel data on how patients with different strata (levels) of preoperative glycaemic control progress in the postoperative period. Poor preoperative glycaemic control is associated with postoperative complications in retrospective studies [10,11]. If this study confirms an association between poor preoperative glycaemic control and adverse outcomes, then the beginning of personalised perioperative medicine for diabetic patients will be enabled. For example, it is known from intensive care medicine that patients with better pre-admission glycaemic control ( $HbA1c < 53$  mmol.mol) have worse outcomes if they develop hyperglycaemia, compared with patients whose pre-existing glycaemic control was already poor ( $HbA1c > 69$  mmol.mol) [4,11]. If this pattern was reflected in the perioperative management of diabetic patients, it would enable a more personalized approach in the perioperative period. Similarly, whether our other subgroups outlined differ in postoperative outcomes is unknown.

This large, multicentre, international prospective observational study will address these urgent research questions and so create a platform for better management and outcomes for patients undergoing surgery with this high risk, highly prevalent condition, which is increasing in incidence in the European population.

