### 3. OBJECTIVES, ENDPOINTS/OUTCOMES AND OTHER STUDY VARIABLES

#### 3.1 Objectives

1. To document, in a large scale observational, epidemiological study, the perioperative glycaemic management of established diabetic patients undergoing every type of surgery with anaesthesia in Europe.
2. To document the type, incidence and severity of all postoperative complications occurring up to 30 days postoperatively.
3. To document the impact of all complications by determining the number of days at home at 30 days (DAH-30, primary outcome), Comprehensive Complications Index (CCI) score, based on the Clavien-Dindo scale and other secondary outcomes.
4. To undertake sub-group analysis comparing these outcomes among:
  - DM1, DM2 and Other Diabetes ('Other' includes Maturity Onset Diabetes of the Young, (MODY) and LADA and any other type of diabetes).
  - Patients with different strata of pre-operative glycaemic control, i.e. HbA1c <53, HbA1c 53-69 and HbA1c >69 mmol. mmol;[11]
  - Patients who received different anaesthetic techniques:
    - Volatile versus total intravenous anaesthesia.
    - Regional versus general anaesthesia (GA) and
    - Patients receiving combined GA and regional anaesthesia versus GA alone.

A list of the a priori hypotheses is listed in Appendix 9.

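### Wherever the protocol names preoperative HbA1c for analysis it does so in three bands, with no continuous analysis beside them; one should be pre-specified.

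*Protocol*

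**What the plan says.** The main objectives in the Synopsis include: "To evaluate subgroup outcomes, particularly strata of preoperative glycaemic control". Section 3.1 repeats this as a subgroup comparison: "Patients with different strata of pre-operative glycaemic control, i.e. HbA1c <53, HbA1c 53-69 and HbA1c >69 mmol. mmol". Section 7.3.4 carries it into the analysis: "the effects of pre-defined subsets will be investigated. These subsets will include" the bands, given as "Strata of glycaemic control, HbA1c <53, HbA1c 53-69 and HbA1c >69 mmol/mmol", next to diabetes type and anaesthetic technique.

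Section 2.9 explains the interest. It looks ahead to what follows "If this study confirms an association between poor preoperative glycaemic control and adverse outcomes", namely more personalised perioperative care. It also takes the outer cut-points, below 53 and above 69, from an intensive-care observation.

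The main models are in section 7.3.1. Covariates are chosen by screening: "Univariate analyses will be used to help identify variables of potential interest for multivariable analyses, in addition to stepwise selections". Then: "Specific factors, or subsets of interest, will be investigated further using linear mixed models with MLE". That section does not say in what form HbA1c enters any model.

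Section 7.3.5 expects analyses added outside the initial plan to appear in the Discussion as post hoc, not in Results.

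**The concern.** HbA1c is a continuous measurement. In bands, patients at 54 and 68 count as the same while patients at 52 and 54 count as different. If risk changes steadily with HbA1c, the variation inside each band is thrown away and power falls. If risk changes within a band, for example at the low end of the below-53 group, the band average conceals it.

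This matters more here than for a routine covariate, because glycaemic control is the one subgroup factor that the main objectives single out. Timing matters too. Under section 7.3.5, a continuous analysis that is not planned in advance would be expected to sit in the Discussion, so the more informative analysis could be kept out of Results.

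**Working it through.** **Inputs from the protocol.** Cut-points 53 and 69 (sections 3.1 and 7.3.4). N = 5,000, standardised difference 0.15, up to 70 hypotheses, corrected alpha 0.0007, power at least 90% (section 7.1).

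**Assumed.** Two-sided tests. The protocol gives no HbA1c mean, SD, shape or band sizes, so these are varied below. The bands are read in mmol/mol.

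**1. The plan's own figure.** 0.05/70 = 0.000714, which agrees with 0.0007. For two groups of 2,500, z = 0.15/√(2/2500) = 5.30. The critical value is 3.39, so power = Φ(5.30 − 3.39) = 97%. The statement of at least 90% is reproduced for an even two-way split. It does not carry over to pairs of HbA1c bands at the same effect and alpha:
- Equal thirds: 83% for each pair.
- An assumed 50/30/20 split: 89%, 73% and 61%.

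**2. Information kept by the bands.** For a linear relation, the efficiency of three groups relative to a continuous linear term is R = Σ pₖ(mₖ − m)²/s². Here pₖ and mₖ are the share and mean of band k, and m and s are the overall mean and SD.

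Log-normal, mean 55, SD 12: shares 0.475, 0.402, 0.123; band means 45.19, 59.80, 77.11.
R = (0.475×9.81² + 0.402×4.80² + 0.123×22.11²)/144 = 115.1/144 = 0.80.

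| Mean / SD | Share <53 | Share 53-69 | Share >69 | R |
|---|---|---|---|---|
| 55 / 12 | 47% | 40% | 12% | 0.80 |
| 57 / 15 | 44% | 37% | 19% | 0.80 |
| 60 / 18 | 39% | 34% | 27% | 0.78 |
| 62 / 20 | 37% | 32% | 31% | 0.75 |

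Over means of 50-65 and SDs of 10-20, R is 0.67-0.81 (normal), 0.73-0.81 (log-normal) and 0.67-0.80 (shifted log-normal). For a normal exposure, three groups lose at least 19% even at the best cut-points.

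**3. Where the loss sits.** With a normal exposure cut into equal thirds, each open-ended band holds about 9.3% of the total variance as lost within-band variation, against 2.0% in the middle band.

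**4. Power, charging each method its degrees of freedom.** At alpha 0.05/70, a 1-df test with 90% power has noncentrality (3.384 + 1.282)² = 21.77. Chi-square critical values are 11.45 (1 df), 14.49 (2 df) and 16.98 (3 df). A spline contains the linear term, so under a linear truth it keeps the full 21.77. The bands keep 21.77 × R.

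| Analysis | df | Noncentrality | Power |
|---|---|---|---|
| Linear term | 1 | 21.77 | 90% |
| Spline, 3 knots | 2 | 21.77 | 84% |
| Spline, 4 knots | 3 | 21.77 | 78% |
| Three bands, R = 0.75 to 0.80 | 2 | 16.4 to 17.4 | 65% to 69% |

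The 3-knot spline and the three bands use the same 2 df, so the gap of 15 to 19 points comes entirely from the information that banding discards.

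**The case against.** The strongest reply is that functional form usually belongs in the statistical analysis plan, which was not available, and that the a priori hypotheses are in Appendix 9, also not available. This stands in part. Either document may already contain a continuous analysis. But the protocol is not silent: it names three bands as the pre-defined form, and section 7.3.5 makes that choice consequential.

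A second reply is that the bands match the objective as worded, are fixed in advance, are consistent across sections and rest on cited literature. That is correct, and it is a reason to keep them. It is not a reason to have nothing beside them.

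Several stronger readings are tempting and are not supported:

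- *That HbA1c will be analysed only in bands.* Section 7.3.1 leaves its form in the main models open and speaks of factors as well as subsets. The list in 7.3.4 is also not closed.
- *That the below-53 band is the largest.* Within the same log-normal range its share runs from 24% (mean 62, SD 12) to 53% (mean 55, SD 20). In the first case it is the smallest band.
- *That residual confounding follows.* Nothing in the protocol says that HbA1c will be an adjustment variable, or a banded one.
- *That a U-shape would be missed.* Three unordered bands can show a U-shape across bands. Only the shape within a band is hidden.
- *That the fix recovers the equivalent of 20-25% of patients.* That comparison is with a 1-df linear term. A spline gives some of it back through its extra degrees of freedom. The efficiency figure also presumes linearity and does not apply to a curved relation.

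**Conclusion.** The point holds in a limited form. In the text available, HbA1c is named for analysis only as three bands, for a factor singled out in the main objectives, and no continuous analysis accompanies them. Under the assumed log-normal distributions and a linear relation, about 20-25% of the information is lost (19-33% across all the shapes tried). At the corrected alpha, power falls to about 65-69% where a 3- or 4-knot spline would have 84% or 78%.

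These sizes rest on HbA1c distributions that the documents do not give. The inability to show shape within a band does not depend on them. Nothing in the plan is invalidated: the banded comparisons remain legitimate but are less efficient and less informative than they could be. The change should be made, and it is inexpensive.

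**What to change.** In section 7.3.4, pre-specify an analysis of continuous HbA1c on DAH-30 using a restricted cubic spline with 3 or 4 knots, fixing the number in advance. Include an overall test of association and a test of non-linearity, and state that the analysis is reported in Results. Keep the three bands for descriptive tables and clinical presentation. If the statistical analysis plan or Appendix 9 already specifies this, align the protocol text with it.

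The cost is a few lines of wording and one extra figure, with a headline result less simple than a three-group comparison. No new data are needed provided that the case report form, which was not available, records the HbA1c value and not only the band.
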